9.2 Statistical analyses

9.2.1 Study Population

The data collected in this study will be pooled with all reports of pregnancies collected by the Sponsor which include information on pregnancy outcome. Additional data sources include other past and current clinical trials and spontaneous pharmacovigilance reporting. Pregnancy outcomes will be analyzed on the pooled dataset.

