4.2.2 Completion of the Woman on-line questionnaires by the woman

There will be one online questionnaires to be completed by women, which will be different from that for HCPs.

A single questionnaire will be completed by the woman, where data on pregnancy diagnosis, exposure to ella®, and if known at the time of the questionnaire completion, the pregnancy outcome. If not known at the time of the first completion, the woman will have the option to get back to the questionnaire and continue its completion when the outcome will be known.

For live birth, woman will also be requested to complete a follow-up questionnaire 4 months after the delivery date (**4-month Follow-Up Woman Form**).

The language of the woman questionnaire will be further adapted to facilitate understanding and format will have functional ergonomics that are permitted by online data entry such as linked questions, drop-down menus, and agenda for fill in dates. In addition, some of the questions will integrate a specific tutorial for helping the declarant to enter appropriate answers. Contents of the information requested in the woman questionnaires are detailed in a specific distinct document submitted to the IRB for its approval prior to implementation.

Women who do not want to provide their HCP contact details, will have the option to contact a referent physician who will be commissioned to follow-up directly with the women. Referent physician will be able to answer their questions and guide them through the questionnaire completion process. The referent physician will not be able to complete the woman questionnaire on their behalf.

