4.3 Inclusion criteria

Women meeting all the following criteria will be considered for admission to the study:

- Pregnant women in the USA, exposed to ella® during the menstrual cycle in which the pregnancy started (treatment failure) or at any time during pregnancy (inadvertent exposure during pregnancy)
- Written informed consent provided:
 - When the questionnaire is completed by the HCP, the ICF will be downloaded from the website and 2 print-out copies signed by the woman. One signed copy will be given to the woman for her records.
 - When completed by the woman, an electronic signature will be requested on the ICF module and the woman will be requested to save and/or print-out the ICF for her records.

5 INFORMATION ON ella® SUPPLY

HRA Pharma will not supply any medication. Women will be enrolled after having taken commercially available ella®.

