8.2.2.2 Completion of the Pregnancy and Outcome Forms

- Access the on-line questionnaire
- Provide first 3 characters of her last name and first character of her first name, date of birth, e-mail address (which will be blinded to the sponsor), her weight and height
- Provide information on pregnancy [including date of diagnosis, date of LMP, date and results of ultrasound (if applicable), expected delivery date]
- Provide data on ella® exposure (date of ella® intake, number of tablets taken, time from unprotected intercourse to ella® intake, pregnancy stage at exposure, additional ella® intake)
- Provide relevant concomitant medications taken during the pregnancy, including hormonal contraception or folic acid at the time of conception
- Report any relevant medical condition preceding or during pregnancy (e.g. diabetes, hypertension)
- Provide the pregnancy outcome observed [live birth (including healthy baby, congenital anomaly, neonatal death), pregnancy loss (including spontaneous abortion, ectopic pregnancy, therapeutic abortion, intermediate or late fetal death)]
- Provide recreational drug use (tobacco, alcohol, illicit drugs), if any
- Provide HCP details*. If the woman is not willing to provide her HCP details, she will be invited to contact a referent physician for assistance in the completion of the questionnaire
- Save and submit the questionnaire
- A unique patient number will be sent by e-mail to the woman, to be used for further access to the website. The woman will be able to further access her file at any time by using her unique patient number and continue the questionnaire completion when additional follow-up data is known.

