8.4 Methods of data collection

Online questionnaires for data collection will be available on a dedicated and secured website. Once submitted, these questionnaires will be received by the Sponsor's drug safety department.

Specific questionnaires may be completed on-line either by the HCP or directly by the woman at any time from pregnancy diagnosis up to known pregnancy outcome.

There will be a specific on-line questionnaire to be completed by the HCP where data on pregnancy diagnosis and exposure to ella® will first be collected. Once the pregnancy outcome is known, the HCP will be requested to complete the rest of the questionnaire.

For live birth only (except for neonatal death), HCP will be requested to complete a follow-up questionnaire 4 months after the delivery date (**4 month Follow-Up HCP Form**).

When completed directly by the woman, the woman will have to complete a simplified questionnaire where data on pregnancy diagnosis, exposure to ella®, and if known at the time of the questionnaire completion, the pregnancy outcome.

For live birth only (except for neonatal death), the woman will be encouraged to fill in a 4-month Follow-Up Form around 4 months after the delivery date (**4 month Follow-Up Woman Form**).

The on-line questionnaires together with instructions will be available in English for the HCP and in both English and Spanish for the woman.

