9.2.2.2 Primary Objective Assessments

The primary objective of this observational study is to estimate the rates of occurrence of outcomes of pregnancies exposed to ella® in order to detect a possible signal of concern for adverse outcomes related to exposure to ella®.

Each pregnancy outcome will be described by proportions (cumulative incidence/prevalence) with exact 95% confidence interval.

For each pregnancy outcome, data from all sources (past and current clinical trials, registry, spontaneous pharmacovigilance reporting) will be used. Outcomes to be evaluated are defined as follows:

All Induced abortions (due to a medical/non-medical reason):

Proportion of normal-appearing pregnancies (with analysable ultrasound results) before induced abortion = number of normal-appearing pregnancies with ultrasound compatible with normal growth and development/ number of pregnancies with analysable ultrasound results.

Therapeutic abortion (medical indication)

Proportion of therapeutic abortions = number of therapeutic abortions / number of pregnancies

Birth outcomes

Proportion of live births = number of live births/ total number of births

Proportion of healthy babies = number of live births without any anomaly (healthy babies) / number of deliveries

Total live birth prevalence of congenital anomalies = number of live births with congenital anomalies / number of live births

Proportion of neonatal deaths = number of neonatal deaths / number of live births

Congenital anomalies:

Total prevalence of congenital anomalies = total number of congenital anomalies (terminations of pregnancy for fetal anomaly (TOPFA), stillbirths, live births with congenital anomalies / total number of births (live births + stillbirths)

Pregnancy loss outcomes

Proportion of spontaneous abortions (or spontaneous abortion cumulative incidence) = number of spontaneous abortions / number of pregnancies

Proportion of intermediate fetal deaths* = number of intermediate fetal deaths / number of pregnancies

Proportion of stillbirths (or stillbirth cumulative incidence) = number of stillbirths / number of pregnancies

* more than 20 completed weeks of gestation but less than 28, according to the WHO fetal death classification.

Proportion of ectopic pregnancies (or ectopic pregnancy cumulative incidence) = number of ectopic pregnancies / number of pregnancies with known outcomes reported

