14 DOCUMENTATION AND USE OF STUDY FINDINGS

14.1 Documentation of study findings

The reporting forms will be completed electronically either by the HCP or directly by the woman.

The HCP should complete forms as soon as possible after the pregnancy or its outcome is known.

In case partial information was collected (outcome not known at the time of the questionnaire completion by the HCP) and to ensure that the information on pregnancy course and outcome is correctly received, the HCP will be contacted by the Sponsor or its representative until known pregnancy outcome is obtained, according to the following schedule:

1. First contact at the time of initial declaration receipt
HCP will be reminded that they must complete information on pregnancy outcome
2. Second contact at approximately 20 weeks of woman's pregnancy

- To collect potential information on outcome, if no information was received in the meantime
3. Third contact at the scheduled delivery date
If the pregnancy outcome was not known at the second contact and no information was received in the meantime
 4. Fourth contact 3 months after the date scheduled for delivery
If no information was available at the third contact and no information was received in the meantime
 5. In case of live birth (except for neonate death), HCP/referent physician or the woman (wherever applicable) will be contacted by the Sponsor's drug safety department for safety follow up 4 months after the delivery date.

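### Every primary proportion rests on one all-source pool that can mix pregnancies first reported before and after the outcome was known, so it need not estimate a rate of occurrence

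*Protocol*

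**What the plan says.** **Analysis set.** Protocol 9.2.1: "The data collected in this study will be pooled with all reports of pregnancies collected by the Sponsor which include information on pregnancy outcome". It continues: "Additional data sources include other past and current clinical trials and spontaneous pharmacovigilance reporting. Pregnancy outcomes will be analyzed on the pooled dataset". Section 9.2.2.2 applies this throughout: "For each pregnancy outcome, data from all sources (past and current clinical trials, registry, spontaneous pharmacovigilance reporting) will be used". The synopsis and section 2.1 put the same sources into the primary objective.

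**Purpose.** Section 9.2.2.2 sets out to estimate how often outcomes occur in order to detect a possible signal. The synopsis and 9.2.2.4 compare the proportions with a reference population.

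**Entry to the study.** The design is called prospective, and 4.3 admits "Pregnant women in the USA, exposed to ella® during the menstrual cycle in which the pregnancy started" or at any time during pregnancy. On the woman's route, 4.2.2 collects "if known at the time of the questionnaire completion, the pregnancy outcome" at first completion; otherwise, under 8.2.2.2, she can return and "continue the questionnaire completion when additional follow-up data is known". Section 8.4 lets either kind of reporter complete a questionnaire "at any time from pregnancy diagnosis up to known pregnancy outcome". For HCPs, 14.1 says: "The HCP should complete forms as soon as possible after the pregnancy or its outcome is known". Sections 8.3 and 14.1 give a separate contact schedule to HCPs whose case was entered before the outcome was known.

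**Breakdowns.** The last paragraph of 9.2.2.2 fixes an overall result, results by country and results by age. Section 9.2.2 leaves further detail to the SAP.

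**The concern.** Cases divided by reports is a rate of occurrence only if entry to the denominator does not depend on the outcome. A pregnancy entered while its outcome is open, and then followed, comes close to that. One entered because of how it ended does not. The pool puts both into one numerator and one denominator.

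The exact interval describes sampling error only, and collecting more reports does not remove selection. A test against a reference population could therefore show an excess that is not there, or hide one that is. The case-by-case review by the Data Monitoring Board (section 11) judges relationship to exposure; it does not correct a proportion. The protocol uses the distinction between outcome-known and outcome-open reports when it schedules HCP follow-up, but does not carry it into the primary proportions.

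**Working it through.** **1. Can the pool contain both kinds of report?**
- Woman's route: yes, plainly (4.2.2, 8.4).
- HCP route: implied. A special schedule for cases entered before the outcome was known (8.3), and for cases where the outcome was not known at completion (14.1), presupposes others where it was.
- Spontaneous reports: possible. The documents do not describe their timing.
- Separated in the primary proportions? No. Country and age are the only fixed splits.

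**2. The plan's own figure.** Inputs (9.1 and Annex 1, Table 1): two-sided alpha 0.05, power 80%, exposed to unexposed 1:10 (k = 10), p1 = 6%, p2 = 3%.

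n = [1.96·√((1+1/k)·p̄(1−p̄)) + 0.842·√(p1(1−p1) + p2(1−p2)/k)]² / (p1−p2)², with p̄ = (p1 + k·p2)/(1+k). This gives 361.9. With the continuity correction, n/4·[1 + √(1 + 2(k+1)/(n·k·|p1−p2|))]² = 397.7, so 398 as in Table 1. The same steps for 3% versus 1% give 391.9, so 392, again as in Table 1. The sample-size arithmetic is correct; it has no term for selective reporting.

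**3. Illustration of mixing (all mixes assumed).** Let f be the share first reported with the outcome known, q the adverse share among them, and p the true proportion. Pooled proportion = (1−f)·p + f·q. The chance of significance is Φ[(d − c − 1.96·se0)/se1], with d the difference from the 3% reference, c = ½(1/400 + 1/4000) = 0.001375, and se0 and se1 the standard errors under no difference and under the difference.

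| True p | f | q | Pooled | Apparent RR | Chance of significance |
|---|---|---|---|---|---|
| 3% (no effect) | 10% | 6% | 3.3% | 1.1 | 4% |
| 3% | 25% | 6% | 3.75% | 1.25 | 12% |
| 3% | 25% | 10% | 4.75% | 1.6 | 43% |
| 3% | 50% | 10% | 6.5% | 2.2 | 89% |
| 6% (true RR 2) | 10% | 3% | 5.7% | 1.9 | 73% |
| 6% | 25% | 1% | 4.75% | 1.6 | 43% |
| 6% | 50% | 1% | 3.5% | 1.2 | 7% |

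Without mixing, a true RR of 2 has 80% power at 400: (0.03 − 0.001375 − 1.96×0.00933)/0.01218 = 0.85, and Φ(0.85) = 0.80.

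To mimic an RR of 2 with no effect, q = (0.06 − (1−f)·0.03)/f, which is 33% at f = 10%, 15% at f = 25% and 9% at f = 50%. Adverse outcomes would then have to be reported about 16, 6 and 3 times as readily as normal ones ([q/(1−q)]/[0.03/0.97]).

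**4. Price of looking at the outcome-not-known group (numbers assumed).**

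| Cases | Power, 3% vs 6% | Exact 95% interval around 3% |
|---|---|---|
| 400 | 80% | 1.6–5.2% |
| 200 | 53% | 1.1–6.4% |
| 100 | 31% | 0.6–8.5% |

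**The case against.** **The SAP may deal with it.** It may add a split by source or timing, and 9.2.1 does not forbid one. That is why the absence of a breakdown is not the point. The point is that the protocol itself names the pool as the set for every primary proportion.

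**Pooling is a declared choice with a reason.** Section 1 reports eight pregnant women from 219 European sites and no participating US site. This stands: cases are scarce, and the pool should still be reported.

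**The HCP evidence is softer.** Sections 4.2.1 and 8.4 describe diagnosis and exposure first and outcome later, and the wording in 14.1 could refer to two successive forms. This stands in part: outcome-known entry is explicit only for women and implied for HCPs.

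**There are partial safeguards.** The study is US-only and the registry European, so the country split partly separates sources, and testing is conditional on a suitable reference. Neither separates reports by timing.

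**The size is assumed.** This stands in full. A reader might infer from the larger rows of the table that the pooled proportions are biased, probably upwards. The documents give neither f nor q, and some of the mixes need strongly selective reporting that nothing in the protocol supports.

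**A prospective-only primary set would not deliver the rate either.** A reader might infer that restricting the main estimate to outcome-not-known cases settles the matter. It does not. Entry is allowed at any time from diagnosis, so losses before entry drop out and spontaneous abortion can be understated. Women may also report after an abnormal prenatal test, since such results are collected at enrolment (study schedule), so selection on anomalies can remain. Making that smaller set the sole main estimate, at the power shown for 200 or 100 cases, is open to debate.

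**Conclusion.** The point holds as a structural one. Followed as written, the plan can produce a primary proportion that is not a rate of occurrence, with an exact interval that does not reflect this, and no fixed analysis would reveal it. The conclusion rests on the protocol's text and on one condition: that the decision to report depends on the outcome for at least some reports.

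The documents do not show that a bias exists, how large it is or which way it runs. The mixing figures show only that the consequence could be trivial or as large as the effect the study is sized to detect. It is worth fixing because classifying and showing the groups costs little and takes nothing away from the pool.

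**What to change.** Amend 9.2.1 and 9.2.2.2, and align the all-sources sentences in the synopsis and 2.1:

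- Classify each pregnancy from every source by whether the outcome was known at first report: known, not known or unclassifiable.
- Present each primary proportion, exact interval and reference comparison separately for these groups and by source, beside the full pool. Rest signal conclusions against a reference on the outcome-not-known group, with the pool as supportive.
- For spontaneous abortion, take account of gestational age at entry, for example by a left-truncated analysis. For congenital anomalies, add a sensitivity analysis leaving out cases first reported after an abnormal prenatal test.
- State that the 400 counts pooled cases, as 4.1 and 9.2.1 together suggest, and give the power or precision for the outcome-not-known number reached.
- Reconcile the inclusion criterion in 4.3, which speaks of pregnant women, with entry once the outcome is known (4.2.2, 8.4, 14.1).

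**Cost.** A protocol amendment. Study cases can probably be classified from what is already tracked: receipt of the initial declaration (14.1) and completion of the outcome part (8.2.1.3, 8.2.2.2). Some older pooled cases may be unclassifiable. The groups are smaller and their intervals wider; at an assumed 200 cases the risk ratio detectable with 80% power at a 3% baseline rises from 2.0 to 2.5. No case is lost from reporting.

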9.2.2 Statistical analysis

All planned analyses will be detailed in the statistical analysis plan.

9.2.2.1 Descriptive analysis

Descriptive statistics (mean, standard deviation, 95% confidence interval for mean, minimum, median, maximum, and number of observations and missing cases) for quantitative variables, and proportions (cumulative incidence or prevalence) for categorical variables will be calculated with binomial or Poisson exact confidence intervals. The proportion of cases that are lost to follow-up will be described.

Baseline characteristics data of enrolled and completed cases will be described: age, pregnancy status at time of ella® exposure, time from unprotected intercourse to exposure in case of treatment failure, or time from LMP to exposure in case of inadvertent use as well as multiple ella® intakes since her LMP.

9.2.2.2 Primary Objective Assessments

The primary objective of this observational study is to estimate the rates of occurrence of outcomes of pregnancies exposed to ella® in order to detect a possible signal of concern for adverse outcomes related to exposure to ella®.

Each pregnancy outcome will be described by proportions (cumulative incidence/prevalence) with exact 95% confidence interval.

For each pregnancy outcome, data from all sources (past and current clinical trials, registry, spontaneous pharmacovigilance reporting) will be used. Outcomes to be evaluated are defined as follows:

All Induced abortions (due to a medical/non-medical reason):

Proportion of normal-appearing pregnancies (with analysable ultrasound results) before induced abortion = number of normal-appearing pregnancies with ultrasound compatible with normal growth and development/ number of pregnancies with analysable ultrasound results.

Therapeutic abortion (medical indication)

Proportion of therapeutic abortions = number of therapeutic abortions / number of pregnancies

Birth outcomes

Proportion of live births = number of live births/ total number of births

Proportion of healthy babies = number of live births without any anomaly (healthy babies) / number of deliveries

Total live birth prevalence of congenital anomalies = number of live births with congenital anomalies / number of live births

Proportion of neonatal deaths = number of neonatal deaths / number of live births

Congenital anomalies:

Total prevalence of congenital anomalies = total number of congenital anomalies (terminations of pregnancy for fetal anomaly (TOPFA), stillbirths, live births with congenital anomalies / total number of births (live births + stillbirths)

Pregnancy loss outcomes

Proportion of spontaneous abortions (or spontaneous abortion cumulative incidence) = number of spontaneous abortions / number of pregnancies

Proportion of intermediate fetal deaths* = number of intermediate fetal deaths / number of pregnancies

Proportion of stillbirths (or stillbirth cumulative incidence) = number of stillbirths / number of pregnancies

* more than 20 completed weeks of gestation but less than 28, according to the WHO fetal death classification.

Proportion of ectopic pregnancies (or ectopic pregnancy cumulative incidence) = number of ectopic pregnancies / number of pregnancies with known outcomes reported

These proportions (cumulative incidence) of adverse events and their 95% confidence intervals will be calculated for the overall sample as well as by country, in order to assess potential differences due to variations in clinical practice regarding the management of pregnancies and pregnancy complications. Results will also be presented by age.

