All cases will be managed according to the sponsor's Pharmacovigilance processes, in line with the applicable legislation.

Whenever applicable, individual case safety reports (ICSRs) will be submitted to Health Authorities on an expedited basis according to current regulations.

Progress status updates will be given in each Periodic Safety Update Report (PSUR) and Development Safety Update Report (DSUR) if applicable.

Additionally, a descriptive analysis of the data collected will be provided annually in the PSUR.

Study duration and dates

Recruitment of women will be done using a website access. Implementation of the website is planned for the second quarter of 2014 and website will be in place during the whole course of the study.

STUDY SCHEDULE

Period of pregnancy Study procedures	Enrolment in the study	Pregnancy Course	End of pregnancy	4 months FU ³
Written ¹ informed consent	X			
Inclusion criteria	X			
Pregnancy diagnosis	X			
ella [®] exposure	X			
Prior and concomitant medications	X	X	X	
Recreational drug use (tobacco, alcohol, illicit drugs)	X	X	X	
Serology and prenatal tests results	X			
Medical history	X			
Maternal and fetal pregnancy complication	X	X	X	
Pregnancy outcome ²			X	
Live birth follow-up ³				X

¹: Signed ICF will be collected according to local regulations. When completed by the HCP, prior starting the questionnaire completion, the ICF will be downloaded from the website and a print-out copy signed by the woman. When completed by the woman, prior starting the questionnaire completion, an electronic signature will be requested on the ICF module and the woman will be requested to save and/or print the ICF for her records.

²: Possible pregnancy outcomes are: Live birth (healthy baby, congenital anomaly or other neonatal diagnosis, or neonatal death); pregnancy loss (spontaneous abortion or ectopic pregnancy or induced abortion, premature stillbirth)

³: In case of live birth, the period of observation of the study will last for 4 months post-delivery to access possible congenital anomalies that may not be detected at birth.

ABBREVIATIONS AND DEFINITIONS

ADR	Adverse Drug Reaction
AE	Adverse Event
AFP	Alpha-Fetoprotein
CFR	Code of Federal Regulations
CHMP	Committee for Medicinal Products for Human Use
CRO	Contract Research Organization
DMB	Data Monitoring Board
DSUR	Development Safety Update Report
EC	Emergency Contraception
EUROCAT	European Surveillance of Congenital Anomalies

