8 STUDY PROCEDURES AND SCHEDULE

8.1 Overview of safety data

Pregnancy information

Date of diagnosis, date of LMP, date and results of ultrasound (if applicable) and expected delivery date.

Exposure to ella®

Data on exposure to ella® include date of ella® intake and number of tablets taken, time from intercourse to ella® intake; pregnancy stage at ella® exposure, pregnancy status before ella® intake.

Outcomes

All outcomes and the data collected to assess them are:

- Live birth – gender, birth weight, gestational age, delivery method and Apgar scores will be collected in all cases. For healthy babies and those with congenital anomalies or other neonatal diagnosis, the study observation period will last until 4 months after delivery;
 - Congenital anomaly or other neonatal diagnosis – description of anomaly and possible causes will be additionally collected;
 - Neonatal death (from birth through to 28 completed days of age*) – age at death, possible etiology and result of autopsy if performed will be additionally collected.
- Pregnancy loss – gestational age, possible etiology of pregnancy loss and any complications (vaginal bleeding, need for curettage, infection) will be collected in all cases.
 - Spontaneous abortion (or early fetal death i.e. < 20 completed weeks of gestation*)
 - Ectopic pregnancy
 - Induced abortion (no medical reason – woman's elective choice, elective abortion with fetal defects, or maternal health complications)
 - Stillbirth:
 - Intermediate fetal death (more than 20 completed weeks of gestation but less than 28*)
 - Late fetal death (\geq 28 completed weeks of gestation*).

Maternal health complications of pregnancy

In all cases, relationship of the outcome observed with the exposure to ella® will be assessed by the HCP and according to the standard pharmacovigilance process.

* According to the WHO International Classification of Disease (ICD)

Prior and concomitant medications

Prior and concomitant medications will be collected in the HCP or women questionnaires. Collection period covers the pregnancy duration from LMP to the end of pregnancy.

Other

Maternal family history; recreational drug use (tobacco, alcohol, illicit drugs) and serological and prenatal tests.

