8.2.1.3 Completion of the Pregnancy Outcome Forms

When the outcome of the pregnancy is known*, the HCP will be asked to fill-in the Pregnancy Outcome forms.

- Access the website with the HCP unique user ID and password
- Start the Pregnancy Outcome Form completion
- Collect the pregnancy outcome observed [live birth (i.e. healthy baby, congenital anomaly, neonatal death) including pregnancy complications, pregnancy loss (including spontaneous abortion, ectopic pregnancy, therapeutic abortion, intermediate or late fetal death), maternal health complications]
- Collect recreational drug use (tobacco, alcohol, illicit drugs), if any
- Collect relevant maternal and family medical history, including history related to previous pregnancies, including congenital birth defects
- Collect serology and prenatal tests (type, date, results)
- Collect relevant concomitant medications
- Save and submit the forms.

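### The healthy-baby numerator in section 9.2.2.2 does not match the protocol's own live-birth classes: a neonatal death without an anomaly also counts as a healthy baby

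*Protocol*

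**What the plan says.** Among the birth outcomes under the primary objective, Protocol section 9.2.2.2 gives: "Proportion of healthy babies = number of live births without any anomaly (healthy babies"), with deliveries as the denominator. The same list gives "Proportion of neonatal deaths = number of neonatal deaths / number of live births" and "Total live birth prevalence of congenital anomalies = number of live births with congenital anomalies / number of live births". It has no formula for other neonatal diagnoses.

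Elsewhere the protocol divides live births into classes. Footnote 2 of the study schedule reads: "Live birth (healthy baby, congenital anomaly or other neonatal diagnosis, or neonatal death"). Section 8.1 keeps the healthy group separate when it sets follow-up: "For healthy babies and those with congenital anomalies or other neonatal diagnosis, the study observation period will last until 4 months after delivery". It lists as a further class under live birth: "Neonatal death (from birth through to 28 completed days of age"). The professional's outcome form in section 8.2.1.3 records "live birth (i.e. healthy baby, congenital anomaly, neonatal death"), and the woman's form in section 8.2.2.2 lists the same three entries. Neither form description names other neonatal diagnoses.

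**The concern.** The class label and the formula disagree. In the schedule and section 8.1, a healthy baby is what remains after anomalies, other neonatal diagnoses and neonatal deaths are set aside. In section 9.2.2.2 only babies with an anomaly are removed.

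The stated aim of the primary analysis is to detect a possible safety signal. A measure labelled healthy babies that does not fall when a structurally normal newborn dies gives a reassuring figure that its label does not support. Two analysts could also report different values from the same data, one applying the formula and the other counting the recorded class.

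**Working it through.** No figure in the protocol is at stake, so there is none to reproduce. The check sets the formula against the classes and then sizes the gap.

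**Step 1: neonatal deaths.** Section 9.2.2.2 divides neonatal deaths by live births, and section 8.1 lists neonatal death under live birth. Every neonatal death is therefore a live birth. If the baby had no anomaly, it meets the healthy numerator, and nothing in the formula removes it. The same baby enters the neonatal-death numerator. Deaths with an anomaly are already excluded from the healthy count.

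**Step 2: other neonatal diagnoses.** Two readings are open.
- *Narrow:* anomaly means congenital anomaly. A baby whose only finding is another neonatal diagnosis is then scored as healthy.
- *Wide:* anomaly covers the whole combined class in section 8.1. That baby is then excluded. A death also recorded with another neonatal diagnosis drops out too, leaving only deaths recorded with neither.

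**Step 3: size.** Let N = deliveries, L = live births, A = live births with an anomaly, D = neonatal deaths without an anomaly, and O = surviving babies whose only finding is another neonatal diagnosis.
- Formula in section 9.2.2.2 (narrow reading): (L − A)/N
- Class in section 8.1: (L − A − D − O)/N
- Overstatement: (D + O)/N under the narrow reading. Under the wide reading it is D/N, with D limited to deaths recorded with neither finding.

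Neither D nor O can be negative, so the proportion can only be too high.

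**Step 4: illustration.** All inputs are assumed: N = L = 250 (singletons, no stillbirths), A = 5, D = 2. The formula gives (250 − 5)/250 = 245/250 = 98.0%, whatever D and O are.

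| O (assumed) | Healthy by section 8.1 | Overstatement |
|---|---|---|
| 0 | 243/250 = 97.2% | 2/250 = 0.8 points |
| 5 | 238/250 = 95.2% | 7/250 = 2.8 points |
| 25 | 218/250 = 87.2% | 27/250 = 10.8 points |

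The first row is the effect of deaths alone. With D from 1 to 4 it would run from 1/250 = 0.4 to 4/250 = 1.6 points. The second and third rows apply only under the narrow reading. In the third, 25 of the 27 reclassified babies come from the assumed number of other diagnoses.

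**The case against.** The strongest reply concerns other neonatal diagnoses. Section 8.1 puts them in one class with congenital anomalies and, for that whole class, asks the reporter to describe the anomaly. In section 9.2.2.2 the healthy-baby line speaks of any anomaly, while the next line specifies congenital anomalies. The wide reading is therefore reasonable. This stands, and it is why that part of the point is stated conditionally.

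A second reply is that the bracketed words in the formula point to the recorded healthy-baby class, so an analyst would probably count that class, and section 9.2.2 leaves detail to the analysis plan. That may be the intention. However, section 9.2.2.2 already fixes the definition, and its words contradict the class it names.

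A third reply is that little is hidden. Neonatal deaths have their own proportion in the same section. Birth complications are also described case by case, and the Data Monitoring Board, which includes a neonatologist, reviews every reported pregnancy. The healthy-baby proportion drives no sample size calculation and has no decision rule. All of this is correct. It limits the consequence but does not remove the double classification.

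A reader might infer that every neonatal death is scored as healthy, or that the proportion is overstated by 5 to 15 points. The documents support neither. Deaths with an anomaly are excluded, and an overstatement of that size needs both the narrow reading and rates of other neonatal diagnoses that the protocol does not give.

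**Conclusion.** The definition in section 9.2.2.2 conflicts with the live-birth classes in the schedule footnote and section 8.1. The part about neonatal deaths without an anomaly follows directly from the text. The part about other neonatal diagnoses depends on how anomaly is read, which the protocol does not settle.

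The direction is certain: the proportion can only be overstated. The size is not known, because the documents give no rate for either group. Deaths alone give about 0.8 points for an assumed 2 in 250 singleton deliveries, on the further assumption that neither death is excluded by another recorded diagnosis. The overstatement grows if other diagnoses are scored as healthy.

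It would go too far to conclude that the plan is blind to neonatal harm, since deaths are reported separately. This is a definitional inconsistency that should be corrected. It leaves the study's power and its other outcome measures untouched.

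**What to change.** In section 9.2.2.2, define the healthy-baby numerator as live births in the healthy-baby class of section 8.1: no congenital anomaly, no other neonatal diagnosis and no neonatal death. Confirm that both outcome forms record other neonatal diagnoses, because the descriptions in sections 8.2.1.3 and 8.2.2.2 do not name them.

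If the sponsor prefers to keep an anomaly-only numerator, relabel the measure as live births without congenital anomaly, so that it no longer claims to count healthy babies.

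A separate proportion for other neonatal diagnoses is optional, and its absence is not an error.

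The cost is a change of wording, possibly a form entry if the class is not yet captured, and a slightly less favourable healthy-baby proportion.
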